### **Preparation for Visit 2**

Two weeks before the six-month anniversary of Visit 1, staff will contact participant to confirm the Visit 2 appointment time, give instructions for the pre-visit ASE/ACE, and how to report the result. Regardless of prior results, all persons will be asked to return for Visit 2. Persons with a prior contraindication for ASE/ACE will not be asked to complete the Visit 2 ASE/ACE until cleared by a clinician. To reduce loss to follow up, staff will contact participants two days before Visit 2 to encourage attendance.

Participants will complete the Visit 2 pre-exam computer-assisted self-interview before coming to the clinic for Visit 2. The Visit 2 pre-exam CASI will add questions to the Visit 1 pre-exam CASI to assess 1) knowledge retention about how to do an ASE/ACE, 2) use of ASE/ACE between visits, 3) health-seeking behavior if a participant detected an abnormality between

visits,) social desirability bias (to assess response bias related to being compliant about practicing), and social support questions.

After the pre-exam CASI, participants will be asked to do the ASE/ACE at home within 24 hours before the Visit 2 in-clinic visit. ASE/ACE instructions will be provided upon request. The person will then complete an ASE/ACE, record results as either normal or abnormal, and text the result to the study staff as soon as they're done with the anal exam. Persons in the control arm will be asked about performing the ASE/ACE between visits, technique, and frequency to control for potential confounding. Moving the ASE/ACE to a home-based exam will shorten the participant's time in the clinic which, regarding nosocomial infections like coronavirus, supports a safer clinic visit for participants and may encourage more participants to attend the visit.

Participants will complete an online COVID-19 symptoms survey within 24 hours of Visit 2.

## **Visit 2 Study Procedures**

During Visit 2, study staff will confirm the participant's ID, measure their weight and waist circumference, and then room the participant in a private room.

The clinician will collect an anal canal swab using a procedure identical to Visit 1 and provide a DARE. The clinician will immediately give DARE results (with results recorded using the same form from Visit 1) before participants take the post-exam CASI which will explore participant responses to knowledge of false-positive, false-negative, true-positive and true-negative results, e.g., how does a false-positive result impact intention to perform the procedure in the future?

After completion of the post-exam CASI, persons will be paid \$80. They then can leave.

If the health care provider found an abnormality at Visit 2 during DARE that required referral, we will maintain contact with the person to record health seeking behavior, treatment received, if any, and the outcome.

Persons who initially entered the study with a partner, but are no longer partnered at Visit 2, can switch from an ACE to an ASE. These changes will be noted and accounted for in analyses. Persons who conducted an ASE at Visit 1 will be asked to conduct an ASE at Visit 2.

To determine the proportion of consented persons who would be interested in a follow-up anal cancer study, all persons who consented to the parent study using a UChicago ICF or an MCW ICF will be contacted near study end. Persons will be contacted by the email or phone number provided by them in the parent study. If necessary, non-respondents will be contacted up to 3 times starting with their preferred method of contact for the first two contacts and switching to another method for the third contact. After asking the one question in this effort (see Renewal Survey file), we will record a Yes or No in the appropriate REDCap field to record their interest in a future study.

## **Data Collected from Study Participants**

For all data collected in the study, personal health information in items 1-6 below will be kept at the Medical College of Wisconsin (MCW) on a secure internet-based server that meets Health Insurance Portability and Accountability Act privacy standards for health records.

1. For each participant, the study coordinator will document completion of study forms and activities (e.g., consents and anal swabbing) and record height, weight, and waist circumference.
2. The health care provider will record on hard copy the results of DARE on participants. These results may be retained in the clinic and then extracted from the participant record by study staff.
3. Participants will use a one-page form in the clinic to record their detection or non-detection of perianal and anal canal abnormalities at Visit 1. Participant will text their result to a staff member after completing the in-home ASE/ACE.
4. The study coordinator will record the participant's understanding about the location and size of the abnormality.
5. In addition to the eligibility CASI before consenting, participants will complete 4 CASIs during the study, both pre-ASE/ACE/DARE CASIs and post-ASE/ACE/DARE CASIs at each visit.
6. Qualitative interviews will collect some participants' reactions to the ASE/ACE results at Visit 1, participants' suggestions on needed resources after doing the ASE/ACE, and suggestions for modification of training.
7. Staff will collect data between Visit 1 and Visit 2, e.g., practice documentation, ASE/ACE results, and referral completion.
8. Participants consenting with a UChicago or MCW ICF will be contacted to determine their interest in a follow-up anal cancer study.

## BURDEN OF TIME ON PARTICIPANTS DOING THE ASE

Activity	Duration
Pre-Visit 1 - Consenting.	12 min
Pre-Exam Online Survey	8 min
Visit 1	
1. Appointment greeting and photo ID check	1 min
2. Body measurements and COVID-9 symptom check	3 min
3. Anal anatomy and pathology and self-/companion exam education (Visit 1 only)	10 min
4. Anal swab	2 min
5. DARE	2 min
6. Anal-self exam or Anal companion exam	10 min
7. Post-Exam CASI	20 min
8. Results including referral or schedule for treatment if needed	7 min
	Total time
	75 min
Other: for first ~40 persons in each city, second DARE (QA and reliability study)	2 min
Other: estimated 28 persons in each city will have discordant result and clinician will offer to give participant another DARE to adjudicate	2 min
Other: for an estimated 65 persons in each city, a qualitative interview will be done	15 min

Note. Persons in couples doing the ACE at Visit 1 will require about 90 minutes for the visit. For Visit 2, persons will not receive the anal anatomy/pathology and ASE/ACE face-to-face education. Rather, they will be given instructions and asked to do the exam without benefit of a training session with study staff; then the clinician will do a DARE and provide results and any needed referrals during the same face-to face.

Activity	Duration
Immediately before Visit 2	
1. Pre-Visit 2 Pre-Exam Online Survey	10 min
2. Anal-self exam or Anal companion exam	8 min
3. COVID-19 Symptom Online Survey	3 mins
During Visit 2	
4. Appointment greeting, body measurement [weight and waist circumference] ID confirmation	3 min
5. Anal swab, DARE and results with clinician including referral or schedule for treatment if needed	5 min
6. Post-Exam CASI	20 min
	Total clinic time
Other: estimated 25 persons will have discordant result and clinician will offer to give participant another DARE to adjudicate	28 min

## STATISTICAL ANALYSIS

### Aim 1

The central hypothesis is that both ASE and ACE at Visit 1 will have  $\geq 70\%$  sensitivity and  $\geq 90\%$  specificity using the clinician DARE as the gold standard. We will test our central hypotheses at Visit 1 by comparing ASE and ACE sensitivity and specificity to random guessing (i.e., sensitivity and specificity=50%) using a one-sample test for proportion. We will then conduct a test of equivalence using two, one-sided likelihood score tests to compare ASE sensitivity in Houston vs Chicago clinics to determine if the ASE performance is equivalent in each city; thus, we will assess the homogeneity of Houston and Chicago sensitivity before combining results. We focus on sensitivity since this factor performed worse than specificity in the pilot study and had wide confidence limits. Sensitivity will also be stratified by other factors, for example location (anal canal vs perianal) and co-morbidities, to determine the effect on sensitivity. Tests will be two-sided with a 0.05 alpha. We will estimate percent agreement, positive predictive value, negative predictive value and perform receiver operating characteristic (ROC) curve analysis for a binary outcome.

To test our central hypothesis, our pilot data indicate 1) 11% of persons will have condyloma, hemorrhoids, skin tags, scars, or malignant tumors at Visit 1 at the anal canal or perianal region, and 2) a sensitivity of  $\geq 70\%$  on ASE and 78% on ACE and specificity  $\geq 90\%$  for both at Visit 1. Given a null value for sensitivity and specificity of 50% (since we seek to rule out accuracy due only to chance), our power to detect sensitivity  $\geq 70\%$  among 600 individuals is 0.90 and 0.81 among 200 couples. Power to detect specificity  $\geq 90\%$  among both individuals and couples is  $>0.90$ . For multiple comparisons we will use the False Discovery Rate. Using a test of equivalence, our hypothesis of no difference in ASE sensitivity between Houston and Chicago assumes that a difference of less than 0.15 constitutes equivalent sensitivity given that a smaller difference may have little practical relevance for adjusting the protocol in either city. Under this definition of equivalence, we have at least 0.87 power to detect a lack of equivalence in sensitivity between the cities if the actual observed difference ranges from 0 to 0.05. Power was assessed with PASS13.

Qualitative data at Visit 1 will be analyzed with concurrent mixed-methods design, i.e., a participant's study ID number will link qualitative to quantitative data. Demographic characteristics and summary statistics from the CASIs involving quantitative cognitive and affective responses to the ASE/ACE of the ~125 persons getting a qualitative interview will be imported into Atlas.ti (Scientific Software Development GmbH, Berlin, Germany). During qualitative analysis, the imported quantitative data will be used to stratify the 125 persons by demography or other categorical data. Qualitative data will be analyzed as it is collected, per the constant-comparative method. Specifically, as interviews are completed, transcripts will be entered into Atlas.ti for analysis within ~72 hours. Faculty and a graduate research assistant team will independently code the data, meet to compare codes, and resolve discrepancies by collapsing and reorganizing codes to arrive at a common codebook. The researchers will then use axial coding to identify relationships between codes. To arrive at an explanatory model, the team will compare findings and recommendations to the existing literature, and consult CAB members for interpretation. The final explanatory model will aid in understanding how anal cancer knowledge and perceived risk for anal cancer affects ASE/ACE performance. In particular, we will explore anxiety among persons with false-positive results because the false-

positivity rate was 14% among persons in the pilot study who said anal cancer concerned them “a lot,” while among persons who had no, little, or some concern, the false positivity rate was 5% ( $p=0.58$ ) suggesting that anxiety may play a role in false-positive results.

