## BACKGROUND

Anal cancer is a common cancer among gay, bisexual and other men having sex with men (MSM). Its annual incidence is approximately 50-fold and 5-fold higher among HIV-positive MSM and HIV-negative MSM, respectively, compared to the rest of the general population. Like cervical cancer, it is primarily caused by human papillomaviruses (HPV). Unlike cervical cancer, there is no efficacious treatment for anal precancers as there is for cervical precancers. To date, randomized clinical trials have failed to find an efficacious treatment although other trials continue; thus, professional societies recommend an annual Digital Anal Rectal Exam (DARE) for detection of anal abnormalities, including small tumors, among all MSM. But DARE is underutilized, e.g., most persons, regardless of HIV do not receive an annual DARE and most HIV physicians do not perform the exam. Therefore, alternative methods for early detection are needed because early detection of small tumors is associated with >85% 5-year survival.

To increase detection of anal canal tumors, our NCI-funded phase II pilot study in Houston, Texas determined it was feasible to teach MSM to palpate their own, or their companion's, anal canal. Acceptability was 94% among 148 individuals doing the exam on themselves (anal self-exam, ASE) and 92% among 52 couples doing the exam on their companion (anal companion

exam, ACE). There was 93% concordance between the clinician's gold-standard DARE and the participants' ASE or ACE for any anal canal abnormality.

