## **STUDY PURPOSE**

The long-term goal of the Prevent Anal Cancer (PAC) Palpation Study is to decrease morbidity and mortality from anal cancer by increasing detection of anal canal tumors through self- or partner-palpation of the anal canal.

Having established feasibility among MSM to detect an anal abnormality, next steps are to derive robust estimates of accuracy for both ASE and ACE (e.g., increased sample size in the current study), assess if another clinic can replicate the R21 finding (i.e., UChicago), and assess cost-effectiveness of these exams. In this protocol, "accuracy" is a general term for test operating performance and predictive value. It includes our outcomes of concordance, sensitivity, specificity, positive predictive value, and negative predictive value.

Our central hypothesis is that both ASE and ACE at Visit 1 will have  $\geq 70\%$  sensitivity and  $\geq 90\%$  specificity compared to the clinician DARE gold standard; thus, we believe this study will demonstrate that MSM can recognize when disease is present. We will test the hypothesis with three specific aims:

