## **AIMS**

### **Aim 1: Estimate ASE and ACE sensitivity and specificity.**

Hypothesis: ASE and ACE sensitivity will be  $\geq 70\%$  and  $\geq 78\%$ , respectively, at Visit 1; specificity will be  $\geq 90\%$  on both exams, and there will be no difference in ASE sensitivity between Houston and Chicago clinics.

Objective: Our objective in this aim is to compare the men's ASE or ACE result with the clinician gold-standard DARE to determine sensitivity and specificity for each exam at two time points.

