## **SAMPLE SIZE**

800 participants completing Visit 1: 400 in Chicago and 400 in Houston

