For the Aim 2 hypothesis, that practice will be associated with concordance in all persons at Visit 2, sample size will be adjusted downward by dropouts and non-resolving abnormalities from Visit 1. We expect 11% of persons ( $n=88$ ) to have an abnormality at Visit 1 (based on pilot data) with most of these being hemorrhoids and condyloma. We conservatively expect 50% of hemorrhoids and condyloma to resolve in 9 months; thus, there will be a minimum of 44 non-resolving events from Visit 1 and another 10% of persons will dropout ( $800-44=756$ ;  $756-76=680$ ). We have 80% power to detect an odds ratio of at least 1.55 or larger if concordance is 85% and  $n=680$ .

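### Aim 1 tests its 70%/78% sensitivity and 90% specificity hypotheses against 50%, so a specificity result that excludes 90% still passes, and no rule ties a claim to the targets

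*Combined protocol and SAP*

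**What the plan says.** Study Purpose gives the targets in the sentence that begins "Our central hypothesis is that both ASE and ACE at Visit 1 will have": sensitivity at least 70% and specificity at least 90% for both exams, against the clinician's exam (DARE). The Aim 1 hypothesis, which begins "Hypothesis: ASE and ACE sensitivity will be", keeps 70% for ASE, raises ACE sensitivity to 78%, and sets 90% specificity for both.

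Statistical Analysis, Aim 1, restates the 70% and 90% targets and continues "We will test our central hypotheses at Visit 1", the method being "comparing ASE and ACE sensitivity and specificity to random guessing (i.e., sensitivity and specificity=50%) using a one-sample test for proportion". The power paragraph explains the null value: "since we seek to rule out accuracy due only to chance". Tests are two-sided at 0.05, with False Discovery Rate control for multiple comparisons. In that section 70%, 78% and 90% serve only as the hypothesis and as the alternatives for power. Percent agreement, predictive values and an ROC analysis are planned. No confidence interval is specified for sensitivity or specificity, although Aim 2 does specify 95% intervals for its odds ratios.

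**The concern.** Two different statements share one test. The first is that the exam does better than chance. The second is that it reaches a stated level of accuracy. A test against 50% can support the first. It has no bearing on whether the second is met, because a specificity of 60% and one of 95% both lead to rejection. Since the plan names this comparison as the test of its hypotheses, a significant result could be reported as support for specificity of at least 90% when the data exclude that value. The descriptive estimates would show the observed figure, but no pre-specified criterion says when a target may be claimed.

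**Working it through.** **Inputs.** From Statistical Analysis, Aim 1: 11% prevalence of abnormality, 600 individuals, 200 couples, null 0.50, two-sided 0.05. From Sample Size: "800 participants completing Visit 1: 400 in Chicago and 400 in Houston". Since 600 + 200 = 800, the 200 is read as persons. The Aim 2 sample-size text agrees, expecting 88 persons "to have an abnormality at Visit 1 (based on pilot data": 0.11 × 800 = 88. The denominators are therefore:

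- ASE: 0.11 × 600 = 66 abnormal, 534 normal.
- ACE: 0.11 × 200 = 22 abnormal, 178 normal.

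The calculations enumerate the binomial distribution, without FDR adjustment and ignoring correlation within couples. Intervals are exact (Clopper-Pearson) 95%; this is an assumption, because Aim 1 names none.

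**The plan's own power.** The pass mark is the smallest x with P(X ≥ x | n, 0.5) ≤ 0.025 (exact), or with (x/n − 0.5)/√(0.25/n) ≥ 1.96 (z).

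- ASE sensitivity, n = 66: pass mark 42 (exact) or 41 (z). Power at 70% is 0.895 or 0.935; stated 0.90.
- ACE sensitivity, n = 22: pass mark 17 (exact) or 16 (z). Power at 78% is 0.649 or 0.807; stated 0.81. At 70% it is 0.31 or 0.49.
- Specificity at 90%: power about 1.00 for both exams; stated above 0.90.

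The stated powers thus belong to the test against 50%, although no single rule gives both sensitivity figures. The couples' 0.81 arises at a true 78%, not at the 70% named in the same sentence.

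**What a pass allows for specificity.** The band below runs from the exact pass mark to the largest count whose upper limit is under 0.90.

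| | ASE (n = 534) | ACE (n = 178) |
|---|---|---|
| Lowest pass (exact 95% CI) | 291, 54.5% (50.2–58.8%) | 103, 57.9% (50.3–65.2%) |
| Highest pass that excludes 90% (exact 95% CI) | 466, 87.3% (84.1–89.97%) | 151, 84.8% (78.7–89.8%) |
| P(pass) at true 60% | 0.996 | 0.75 |
| P(pass and CI below 90%) at true 85% | 0.94 | 0.51 |
| Same, at true 86% | 0.82 | 0.36 |
| Same, at true 90% | 0.024 | 0.019 |

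The z pass mark is 290 for ASE and again 103 for ACE. The 86% row corresponds to the 14% pilot false positivity among the most concerned participants (Aim 1, qualitative analysis), if that rate was taken among normal clinician exams.

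**Sensitivity.** ASE passes at 41–42 of 66 (62–64%), and a true 65% passes with probability 0.65 (exact) to 0.73 (z). No passing result excludes 70%: the largest count with an upper limit below 70% is 38 of 66, under the pass mark. ACE must already reach 16–17 of 22 (73–77%) to pass.

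**What is expected.** Background reports, in the sentence that begins "There was 93% concordance between the", 93% agreement with the clinician. From 0.93 = 0.11 × sensitivity + 0.89 × specificity, specificity is (0.93 − 0.11 × 0.70)/0.89 = 0.958, or (0.93 − 0.11 × 0.78)/0.89 = 0.949.

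**If 200 couples meant 400 persons** (44 abnormal, 356 normal), ACE specificity would pass at 197 of 356 (55%), counts from 197 to 308 would pass while excluding 90%, and a true 60% would pass with probability 0.967. The conclusion is the same.

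**The case against.** The strongest reply is that the plan never says rejecting 50% establishes 90%. It discloses the null and its reason, Aim 1 is titled as estimation, and an observed 85% would be published as 85%. No stopping rule or later step depends on the p-value, and Aim 3 takes accuracy as a parameter with sensitivity analyses. The troubling outcome is also remote on the plan's own figures: at a true specificity of 95%, passing with an interval below 90% has probability about 3 × 10⁻¹² for ASE and 3 × 10⁻⁷ for ACE. Finally, a lower-limit rule is demanding: if specificity is exactly 90%, it succeeds only 1.9% (ASE) or 1.3% (ACE) of the time.

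Much of this stands. Ruling out chance is a legitimate purpose, and the probabilities at 60% or 85% show what the test cannot exclude, not what is likely. But a favourable expectation does not supply a rule. If Aim 1 is estimation, the plan should commit to intervals and stop calling the 50% comparison the test of its hypotheses; it does neither. The low success rate at a true 90% is inherent in asking data to demonstrate a bound that the truth only just meets. It is a reason to report estimates plainly, not to let a test against 50% stand in for the target.

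**Conclusion.** The concern holds. The stated test cannot support the stated hypothesis, and no other criterion in Aim 1 does so. The effect is largest for specificity of both exams, where a wide band of results passes while contradicting the 90% target. It is smaller for ASE sensitivity, where a pass can fall below 70% but cannot exclude it, and slight for ACE sensitivity. The counts rest on 11% prevalence, 200 persons in couples, independent observations, exact intervals and unadjusted 0.05 tests. Treating all four tests at 0.0125, as a worst case for multiplicity, moves the specificity pass marks only to about 55% (ASE) and 59% (ACE). This should be fixed, because it concerns the central hypothesis and a change of text is enough.

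**What to change.** 1. State that the 50% tests support only a value above 50%, and that chance is ruled out for an exam when both its sensitivity and its specificity tests are significant.
2. Report exact 95% intervals for sensitivity and specificity of each exam beside the targets.
3. Claim specificity of at least 90% only if the lower exact limit reaches 90%. At the planned denominators this needs 495/534 for ASE (lower limit 90.15%) and 169/178 for ACE (90.6%).
4. Treat the sensitivity targets as estimation. Do not call one demonstrated unless the lower limit reaches it: 54/66 for ASE at 70%, 20/22 for ACE at 70%, 22/22 for ACE at 78%.
5. State one ACE sensitivity target in Study Purpose, Aim 1 and the power text, and tie the 0.81 to 78%. The two targets do not contradict each other, but the power sentence names only 70%.

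**Cost.** SAP wording and intervals, with no new data; the downside is a less favourable claim. The specificity rule is practical for ASE (power 0.65, 0.91 and 0.99 at a true 93%, 94% and 95%) and moderate for ACE (0.37, 0.60 and 0.82 at 94%, 95% and 96%). Demonstrating the sensitivity targets is unlikely at this size, hence item 4: ASE 70% has probability 0.02, 0.28 and 0.82 at a true 70%, 78% and 85%; at a true 78%, ACE has 0.11 for the 70% target and 0.004 for the 78% target.

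### Aim 1 treats 50% sensitivity and 50% specificity, each tested alone, as chance; chance is Se + Sp = 1, so neither test alone supports a claim about guessing

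*Combined protocol and SAP*

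**What the plan says.** The central hypothesis (STUDY PURPOSE, and STATISTICAL ANALYSIS, Aim 1) is that both exams reach at least 70% sensitivity and at least 90% specificity against the clinician DARE at Visit 1. The AIMS section sets ACE sensitivity at 78% or more. The hypothesis is to be tested by "comparing ASE and ACE sensitivity and specificity to random guessing (i.e., sensitivity and specificity=50%) using a one-sample test for proportion". The power paragraph repeats the 50% null and gives the reason: "since we seek to rule out accuracy due only to chance". It also says that "Tests will be two-sided with a 0.05 alpha".

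The planning inputs are that "11% of persons will have condyloma, hemorrhoids, skin tags, scars, or malignant tumors at Visit 1", with sensitivity of 70% (ASE) and 78% (ACE) and specificity of 90%. Stated power for sensitivity "among 600 individuals is 0.90 and 0.81 among 200 couples"; for specificity it exceeds 0.90 in both groups.

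Multiple comparisons are handled by the False Discovery Rate. Percent agreement, predictive values and a ROC analysis for a binary outcome are to be estimated, without a null value or decision rule. Nothing says that the sensitivity and specificity tests must both be passed.

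**The concern.** The plan offers 50% as chance itself, not as a minimum acceptable performance. Someone who ignores what they feel and calls abnormal with probability q has sensitivity q and specificity 1 − q. Only a coin-flipper (q = 0.5) sits at 50/50. With about 11% of people abnormal, calling nearly everything normal is a natural uninformed strategy, and it gives high specificity for free. At the plan's expected specificity of 90%, the chance value of sensitivity is 10%, not 50%.

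What is at stake is the meaning attached to each result. A significant specificity test could be reported as better than guessing when it shows nothing of the kind. A non-significant sensitivity test could be reported as no better than guessing when the same data exclude guessing clearly.

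**Working it through.** **Inputs** (STATISTICAL ANALYSIS, Aim 1; SAMPLE SIZE). Two-sided alpha 0.05, null 0.50, prevalence 11%. The 200 is read as persons in couples, because 600 + 200 = 800, the stated total.
- ASE: 0.11 × 600 = 66 abnormal, 534 normal.
- ACE: 0.11 × 200 = 22 abnormal, 178 normal.

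Partners are treated as independent. A test is passed when the count correct reaches the upper cutoff, and power is the binomial upper tail from that cutoff.

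**Step 1: the plan's own power**

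| Test | True value | Cutoff | Power | Stated |
|---|---|---|---|---|
| ASE sensitivity | 70% | exact, ≥42/66 | 0.895 | 0.90 |
| ACE sensitivity | 78% | z, ≥16/22 | 0.807 | 0.81 |
| ACE sensitivity | 78% | exact, ≥17/22 | 0.649 | 0.81 |
| Specificity, both | 90% | exact, ≥291/534 and ≥103/178 | about 1.00 | >0.90 |

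The stated figures are reproduced for the null used. The 0.81 for ACE needs 78% sensitivity and the z cutoff. At 70%, the value in the central hypothesis, ACE power is 0.31 (exact) or 0.49 (z).

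**Step 2: the specificity test under pure guessing (Se = q, Sp = 1 − q)**

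| q | Pass, n = 534 | Pass, n = 178 |
|---|---|---|
| 0 (always normal) | 1.00 | 1.00 |
| 10–11% | about 1.00 | about 1.00 |
| 30% | about 1.00 | 0.9998 |
| 40% | 0.996 | 0.746 |
| 50% | 0.021 | 0.021 |

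The test holds its error rate only at the coin-flip point. The sensitivity test alone has the mirror-image problem: a guesser with q = 70% passes it with probability 0.895 (n = 66), at 30% specificity.

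**Step 3: the sensitivity test when the exam is informative (Sp = 90%, so chance Se = 10%)**

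| True Se | J = Se + Sp − 1 | Exact test vs 50%, ASE | Exact test vs 50%, ACE | Fisher test, ACE |
|---|---|---|---|---|
| 50% | 0.40 | 0.018 | 0.009 | 0.985 |
| 60% | 0.50 | 0.319 | 0.072 | >0.99 |
| 70% | 0.60 | 0.895 | 0.313 | >0.99 |
| 78% | 0.68 | 0.998 | 0.649 | >0.99 |

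Illustrative ACE result: 13/22 abnormals and 160/178 normals called correctly. The exact test of 13/22 against 50% gives p = 0.52. Fisher's test on the table (13, 9; 18, 160) gives p = 0.0000005. J = 0.591 + 0.899 − 1 = 0.49, and AUC = (0.591 + 0.899)/2 = 0.745. The standard error of J is √(13·9/22³ + 160·18/178³) = √(0.01099 + 0.00051) = 0.107, so the 95% CI is 0.49 ± 1.96 × 0.107 = 0.28 to 0.70.

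**Step 4: the two tests together.** Se > 0.5 and Sp > 0.5 imply Se + Sp > 1. The largest probability over all q that a guesser passes both is 0.0013 for 66/534 (q about 46%) and 0.0005 for 22/178 (q about 44%). For ACE with the z cutoff it is 0.002.

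**The case against.** The strongest reply is that the hypothesis is a pair. Both measures are tested for each exam, and passing both does exclude guessing, as Step 4 shows. That stands. A reader might infer from Step 2 that the Aim 1 tests cannot exclude guessing at all; the documents do not support that, because it is true only of each test read alone. What is missing is a rule that both must be passed. A conjunctive hypothesis does not supply one, and neither does False Discovery Rate control.

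Second, the right joint measure is already planned. For a binary result AUC = (Se + Sp)/2, so AUC = 0.5 is the same null as J = 0. That also stands, but the plan gives the ROC analysis no null or decision rule, and the test it names for chance is the one-sample test.

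Third, a reader might infer that the stated power is wrong. It is not, for the null used: both figures are reproduced at the planned sensitivities. The plan names only a one-sample test for proportion, so the z cutoff behind 0.81 is admissible. Low ACE power at 70% is partly a separate question of which sensitivity was assumed.

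Fourth, it is tempting to replace the 50% sensitivity test by J > 0. That would lower the bar. At 90% specificity, Fisher's test of association has power 0.98 for ASE and 0.66 for ACE at only 30% sensitivity, and 0.91 for ACE at 40%. J > 0 answers the chance question and is no evidence for the 70%/90% hypothesis. As a minimum performance level, 50% is defensible.

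**Conclusion.** The concern holds as a fault in what the 50% null is said to mean. Neither test, read alone, supports a statement about chance. Passing the specificity test is near certain for guessers who call abnormal 10–11% of the time. Failing the sensitivity test is compatible with accuracy far above chance (p = 0.52 against p = 0.0000005 in the ACE example).

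The practical loss is limited. At the planned values (ASE 70%; ACE 78% with a z cutoff) power is about as stated. The loss arises mainly at true sensitivity of about 60% or less, and for ACE already at 70% (0.31 exact, 0.49 z). The estimates of sensitivity and specificity are unaffected.

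This rests on the plan's 11% prevalence and 90% specificity, on reading 200 as persons, and on independence between partners, which the plan does not address for Aim 1.

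**What to change.** 1. Base the better-than-chance claim for each exam on J = Se + Sp − 1 > 0, equivalently AUC > 0.5 from the planned ROC analysis, with a 95% confidence interval that allows for couples in ACE.
2. Keep the two 50% tests, describe them as minimum performance levels, and require both to be passed for each exam. State whether the cutoff is exact or z, since for ACE this moves power at 78% from 0.65 to 0.81.
3. Delete the statements that 50% specificity, or 50% sensitivity, alone represents chance.
4. Do not present J > 0 as evidence for the 70%/90% hypothesis.

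The cost is a change to the analysis text and one added analysis, with no new data. Requiring both tests lowers joint power slightly in principle. At 90% specificity the loss is negligible, because that test has power of about 1.00: for ASE, 0.895 × 1.00 = 0.895.
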